7.1. Discontinuation of Study Intervention

In rare instances, it may be necessary for a participant to permanently discontinue (definitive discontinuation) study intervention. If study intervention is definitively discontinued, the participant will remain in the study for additional data collection, consistent with routine safety monitoring. See the SoA (Section 1.3) for data to be collected at the time of discontinuation of study intervention and follow-up and for any further evaluations that need to be completed.

The following infections lead to study intervention discontinuation: confirmed diagnosis of pneumocystis pneumonia, HIV, and active TB, including hepatitis B and C (as further described in Section 7.1.2).

A participant should be permanently discontinued from the study intervention

- if the participant becomes pregnant during the study
- for safety reasons, in the opinion of the investigator, or
- if the investigator determines that a systemic hypersensitivity reaction has occurred related to study intervention administration, the participant may be permanently discontinued from the study intervention, and the sponsor's designated medical monitor should be notified. If the investigator is uncertain about whether a systemic hypersensitivity reaction has occurred and whether discontinuation of study intervention is warranted, the investigator may consult the sponsor.

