2.3. Benefit/Risk Assessment

The toxicology data for LY3872386 demonstrate an acceptable nonclinical safety profile and margin of safety to support the transition from preclinical status to a clinical single-dose study in healthy participants and a multiple-dose study in patients with AD.

The nonclinical safety profile of LY3872386 is generally consistent with its intended pharmacology. Primary safety concerns predicted from studies with the ADC and the payload are bacterial and other infections, secondary to decreases in lymphoid tissue lymphocytes and circulating blood lymphocytes. Other potential risks identified for LY3872386 in toxicology studies and consistent with GC pharmacology are

- atrophy of skin hair follicles, especially near SC injection sites, potentially leading to thinning hair or hair loss
- suppression of the HPA axis
- increased serum triglycerides, and
- increased serum glucose.

The safety and efficacy associated with modulation of the IL-4/IL-13/IL-4R axis have been evaluated with approved drugs such as dupilumab and tralokinumab, and the safety and efficacy of GCs as a class are well-established. The key safety concerns and PD effects of LY3872386, including infection, conjunctivitis, hypersensitivity reactions, local injection site reactions, and systemic GC exposure from LY3558533 (free payload), will be closely monitored during the clinical study.

As with other immunomodulatory therapies, LY3872386 and prednisone may increase the risk of developing infections, increase the risk of an infection becoming more serious, and/or change the effectiveness of vaccines administered. LY3872386 may also increase the risk of opportunistic infections and the reactivation of latent infections. Participants will therefore be screened for hepatitis B, hepatitis C, HIV, and TB. In addition, all participants should be monitored for symptoms and signs of infection after administration of LY3872386 or prednisone.

Infusion reactions and hypersensitivity reactions are potential risks for all biologics. These risks will be carefully monitored during the dosing period in Parts A and B (the LY3872386 portions of the study), with close observation after infusion and stopping rules that prevent re-challenge of patients/participants with significant hypersensitivity reactions.

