7.1.1. Rules for Stopping Dosing and Enrollment in a Cohort

If any of the following scenarios occur, dosing at the current level and further dose escalation will be interrupted and may resume only following written approval from the sponsor medical monitor:

- A single participant experiences an SAE unless obviously unrelated to LY3872386 administration.
- Severe nonserious AEs considered at least possibly related to the study intervention occurring in 2 participants in Parts A or B within the same cohort, independent of whether or not the events are in the same system organ class.
- Two or more participants per cohort in Parts A or B develop TEAEs or clinically significant changes in laboratory safety that are graded as at least moderate, unless there is an obvious explanation other than study intervention or study procedures for the event(s).

• One or more participants present severe AEs related to IV infusion that are related to LY3872386, and the TEAE does not resolve with a reduced IV infusion rate or supportive care.

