7.1.5.2. Infection-Related Criteria for Temporary Withholding

Temporary withholding of study intervention is required if the participant meets any of the following infection-related criteria during the study:

- Serious or opportunistic infections, as defined in Section 5.2. Study intervention has to be withheld until resolution of all acute clinical signs and symptoms, and completion of all appropriate anti-infective treatment (exception for LTBI, noted below).
- A participant diagnosed with LTBI during the study has to be permanently discontinued from study intervention unless the participant is a candidate for LTBI treatment, and is treated for LTBI as follows:
 - o Study intervention is temporarily withheld for at least the first 4 weeks of LTBI treatment.
 - O After receiving at least 4 weeks of appropriate LTBI therapy (as per World Health Organization or US Centers for Disease Control and Prevention guidelines), if there is no evidence of hepatotoxicity (ALT/AST level must remain ≤2 times ULN) or other treatment intolerance, study intervention may be resumed.
 - The participant must complete appropriate LTBI therapy to remain eligible to receive study intervention.
- HBV DNA results that are reported as positive, or as detecting HBV DNA, but HBV DNA is below the level of quantification. In this situation, the sponsor's designated medical monitor should be contacted regarding the participant's status. HBV DNA testing is to be repeated as soon as it is feasible. If HBV DNA is confirmed as positive, the participant must be permanently discontinued from study intervention.

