8.2.7.1.3. Hypersensitivity

Many drugs, but particularly biologic agents, carry the risk of systemic hypersensitivity reactions. If such a reaction occurs, additional data describing each symptom should be provided to the sponsor in the eCRF.

Sites should have appropriately trained medical staff and appropriate medical equipment available when study participants are receiving the study drug. It is recommended that participants who experience a systemic hypersensitivity reaction be treated per the local standard of care.

If the investigator determines that a systemic hypersensitivity reaction has occurred related to study intervention administration, the participant may be permanently discontinued from the study intervention, and the sponsor's designated medical monitor should be notified. If the investigator is uncertain about whether a systemic hypersensitivity reaction has occurred and whether discontinuation of study intervention is warranted, the investigator may consult the sponsor.

In case of systemic hypersensitivity reactions, defined as anaphylaxis or generalized urticaria, additional blood samples should be collected as described in Appendix 2 (Section 10.2). Laboratory results are provided to the sponsor via the central laboratory.

In the event of drug hypersensitivity reactions (immediate or nonimmediate), up to 3 additional samples will be collected each for PK and immunogenicity at the following time points: as close to the onset of the reaction event as possible, at the resolution of the event if possible, and approximately 30 days following the event.

8.2.8. Hepatic Safety Monitoring, Evaluation, and Criteria for Study Drug Interruption or Discontinuation

This table summarizes actions to take based on abnormal hepatic laboratory or clinical changes.

If this laboratory value is observed	Then		
	Initiate or continue close hepatic monitoring	Initiate comprehensive evaluation	Interrupt or discontinue study drug
ALT or AST ≥3x ULN	X		
ALP ≥2x ULN	X		
TBL ≥2x ULN ^a	X		
ALT or AST ≥5x ULN	X	X	
ALP ≥2.5x ULN	X	X	
ALT or AST ≥3x ULN with hepatic signs or symptoms ^b	X	X	X
ALT or AST ≥5x ULN for more than 2 weeks	X	X	X
ALT or AST ≥8x ULN	X	X	X
ALT or AST ≥3x ULN and TBL ≥2x ULN ^a	X	X	X
ALP ≥3x ULN	X	X	X
ALP ≥2.5x ULN and TBL ≥2x ULN ^a	X	X	X
ALP ≥2.5x ULN with hepatic signs or symptoms ^b	X	X	X

- In participants with Gilbert's syndrome, the threshold for TBL may be higher.

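### Section 2.3 says re-challenge after significant hypersensitivity is prevented, but the visible operative text is inconsistent and contains no clear mandatory rule for the affected participant

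*Protocol*

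**What the plan says.** Protocol 2.3, discussing infusion and hypersensitivity reactions in Parts A and B, names two protections: close observation after infusion, and "stopping rules that prevent re-challenge of patients/participants with significant hypersensitivity reactions".

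The operative text is in four places.

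- **7.1.** The list opens "A participant should be permanently discontinued from the study intervention". Its hypersensitivity bullet is a full sentence with a different verb: "if the investigator determines that a systemic hypersensitivity reaction has occurred related to study intervention administration, the participant may be permanently discontinued". The sponsor's medical monitor is to be notified. Where the investigator is unsure, the sponsor may be consulted.
- **8.2.7.1.3.** The same sentence appears without the 7.1 lead-in: "the participant may be permanently discontinued from the study intervention". A later sentence, on extra blood samples, begins "In case of systemic hypersensitivity reactions, defined as anaphylaxis or generalized urticaria".
- **6.1.3.** If the investigator decides that an infusion should not go on, no further dosing attempts are to be made. A later bullet says that, after a reaction severe enough to end the infusion, later infusions may be given with premedication if the sponsor's physician or clinical pharmacologist agrees.
- **7.1.1.** When a trigger is met, "dosing at the current level and further dose escalation will be interrupted and may resume only following written approval from the sponsor medical monitor". One trigger is "A single participant experiences an SAE unless obviously unrelated to LY3872386 administration".

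Section 8 also asks that immediate safety concerns be raised with the sponsor at once, to decide whether the participant goes on with or stops study intervention.

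**The concern.** The benefit/risk section describes a bar on re-challenge. The sections that a site would actually follow describe a decision. The *may* in 7.1 and 8.2.7.1.3 applies after the investigator has already judged the reaction to be both systemic and drug-related; uncertain cases have their own sentence. So discretion remains in exactly the cases that 2.3 says are covered.

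This is a first-in-human study of a biologic. On the visible text, a Part B participant with drug-related anaphylaxis could be dosed again within protocol once the sponsor had approved or agreed. Ethics committees and investigators who rely on 2.3 would not expect that.

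**Working it through.** No sample size, power or error rate is involved. The check sets the sections side by side and then counts the doses at stake.

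**1. Does 7.1 bar re-dosing?** Not clearly. The lead-in says *should*, and the bullet beneath it says *may*. A reader can take either as governing. The neighbouring general safety bullet depends on the investigator's opinion.

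**2. Does 8.2.7.1.3 settle it?** No. It has only *may*.

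**3. Does 6.1.3?** No. Its line against further dosing attempts could be read as a bar, but the later bullet allows subsequent infusions after a reaction that ended one. The symptom list in 6.1.3 includes bronchospasm, hypotension and angioedema, and 8.2.7.1.2 counts anaphylaxis among infusion-related reactions. No bullet excepts these. A reaction that starts after a completed infusion was neither stopped nor slowed, so the re-infusion bullets do not address it.

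**4. Does 7.1.1?** It pauses dosing but does not exclude the participant. Life-threatening anaphylaxis would be an SAE under 10.3.2, so one case halts dosing at that level unless it is obviously unrelated. Dosing may resume on written approval, and nothing then keeps the affected participant out.

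**5. Do the entry criteria?** No. Criterion 48 excludes Part B patients with earlier hypersensitivity to the active substance or excipients, but Section 5 says that eligibility criteria do not apply continuously.

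**6. Can the protocol write a firm rule for one participant?** Yes. Section 7.1.5.2 says "If HBV DNA is confirmed as positive, the participant must be permanently discontinued from study intervention". Section 6.9.1 requires permanent discontinuation after systemic rescue. Section 7.1.6.2 lists two fasting glucose values of at least 126 mg/dL, with no other obvious cause, under permanent discontinuation. The softer hypersensitivity wording is therefore not just house style.

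**7. Doses at stake.** The input is the IP administration row of each Schedule of Activities. Doses left after a first-dose reaction = planned doses − 1.

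| Part | Dosing visits | Planned doses | Left after first dose |
|---|---|---|---|
| A (1.3.1) | Day 1 | 1 | 1 − 1 = 0 |
| B (1.3.2.1) | V2 to V8 | 7 | 7 − 1 = 6 |
| B (1.3.2.2) | V2, V4, V6, V8 | 4 | 4 − 1 = 3 |

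So the gap has practical effect in Part B. The 2.3 statement does not extend to prednisone in Part C.

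**The case against.** The strongest reply is that this is a drafting slip and not a missing protection. The 7.1 bullet sits under a *should*. The medical monitor is to be notified. The discussion required by Section 8 is aimed at the very decision in question. Most clearly significant reactions would be SAEs, so a single case stops dosing until the sponsor approves in writing. Section 2.3 does not define significant, and the sponsor may reasonably prefer clinical judgement to an automatic rule.

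Much of this stands. A reader might infer that 7.1 offers nothing but *may*; its lead-in shows otherwise.

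A reader might also infer that one participant with nonserious generalized urticaria after an SC dose meets no check at all, or might try to count the approvals needed in each scenario. The documents do not support either step:

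- The Section 8 discussion applies.
- Section 7.1.1 is also triggered by at least moderate treatment-emergent events in two participants of a cohort when there is no other obvious explanation. The second event need not be hypersensitivity.
- Section 8.2.7.1.2 treats large-volume SC dosing as infusion, so 6.1.3 may reach some SC doses.
- Section 6.6.1.2, which 4.1 cites for data review before Part B dosing, is not visible. Parts of 6.6.1 and the comments in the Schedule of Activities are also withheld.

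What does not stand is the idea that these safeguards amount to prevention. Each is a notification, a discussion, an agreement or a pause that can be lifted. A rule in withheld text would still conflict with the visible *may*.

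**Conclusion.** The text is wrong as written. Section 2.3 states a protection that the visible operative sections do not clearly provide: 7.1 contradicts itself, 8.2.7.1.3 is permissive, 6.1.3 allows re-infusion without excepting anaphylaxis, and 7.1.1 can be lifted. The safeguards make careless re-dosing unlikely but do not bar it.

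The effect is confined to Part B, with up to 6 or 3 later doses after a first-dose reaction. The documents give no reaction rate, so the number of participants affected cannot be estimated. The conclusion rests on visible text only. It does not imply that the sponsor intends to re-dose such participants. It should be corrected by amendment.

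**What to change.** 1. **7.1 and 8.2.7.1.3.** Replace *may be* with a mandatory sentence, for example: *Study intervention must be stopped permanently in any participant who has anaphylaxis, or any other serious or severe systemic hypersensitivity reaction (including generalized urticaria, angioedema, bronchospasm or hypotension of that grade), that the investigator judges related to study intervention.*
2. **Same sections.** Keep investigator judgement with sponsor consultation for milder or uncertain reactions.
3. **6.1.3.** State that the re-infusion bullets, for both stopped and slowed infusions, do not apply to the mandatory cases. Premedicated re-dosing then stays available for milder reactions such as fever, chills or headache.

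The rule should follow seriousness and severity. The blood-sampling definition in 8.2.7.1.3 would be a poor basis: used alone, it would catch mild generalized urticaria and miss severe angioedema not labelled anaphylaxis. Deleting the *may be* clause in 7.1 and aligning 8.2.7.1.3 would remove the internal conflict but leave only a *should*, which falls short of 2.3. If the sponsor wants to keep full discretion, 2.3 should be reworded to say so.

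The cost is a few wording edits in one amendment, with no new assessments. The downside is that a few Part B participants may lose later doses.

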7.1.1. Rules for Stopping Dosing and Enrollment in a Cohort

If any of the following scenarios occur, dosing at the current level and further dose escalation will be interrupted and may resume only following written approval from the sponsor medical monitor:

- A single participant experiences an SAE unless obviously unrelated to LY3872386 administration.
- Severe nonserious AEs considered at least possibly related to the study intervention occurring in 2 participants in Parts A or B within the same cohort, independent of whether or not the events are in the same system organ class.
- Two or more participants per cohort in Parts A or B develop TEAEs or clinically significant changes in laboratory safety that are graded as at least moderate, unless there is an obvious explanation other than study intervention or study procedures for the event(s).

• One or more participants present severe AEs related to IV infusion that are related to LY3872386, and the TEAE does not resolve with a reduced IV infusion rate or supportive care.

7.1.2. Hepatic Criteria for Study Drug Interruption or Discontinuation

See Section 8.2.8 for hepatic criteria for study drug interruption or discontinuation.

7.1.3. Cardiovascular Stopping Criteria

7.1.3.1. QTc Stopping Criteria

If a clinically significant QTc finding is identified (including, but not limited to, changes from baseline in QTcF after enrollment), the investigator or qualified designee will determine if the participant can continue in the study and if any change in participant management is needed. This review of the ECG printed at the time of collection must be documented. Any new clinically relevant finding should be reported as an AE.

Discontinuation of IP should be considered by the investigator and the sponsor if any of the following occur in a participant:

- QTcF >500 msec
- increase from baseline in QTc >60 msec, from at least 2 consecutive readings

7.1.3.2. Hypertension Stopping Criteria

If 2 consecutive systolic blood pressure \geq 160 mm Hg or if 2 consecutive diastolic blood pressure \geq 100 mm Hg; medical intervention indicated.

7.1.4. Ocular Pressure Interruption Criteria

The following criteria will lead to study intervention interruption:

- >10 points over baseline confirmed by an additional, consecutive assessment conducted prior to treatment administration, or
- >25 mmHg confirmed by an additional, consecutive assessment conducted prior to treatment administration, or
- develops signs of glaucoma

Therapy may resume when ocular pressure is within normal limits and/or sign of glaucoma resolve.

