6.1.3. Management of Infusion Reactions

There is a risk of an infusion reaction with any biological agent. Therefore, all participants should be monitored closely.

Symptoms and signs that may occur as part of an infusion reaction include, but are not limited to:

- fever
- chills
- nausea
- headache
- bronchospasm
- hypotension
- angioedema
- throat irritation
- rash
- pruritus
- myalgia, and
- dizziness.

In the event that a significant infusion reaction occurs, the following guidance should be followed:

• The investigational product infusion should be slowed (for example, reduce the infusion rate by 50% [for example, an infusion rate of 12 mL/h becomes 6 mL/h or slower]) or stopped, depending on the symptoms/signs present:

o if slowed, the infusion should be completed at the slower rate, as tolerated, and

- o if determined by the investigator that the infusion should no longer continue, no further attempts to dose the participant should be made.
- Supportive care should be employed in accordance with the symptoms/signs and consistent with local guidelines.
- If a participant's infusion reaction is sufficiently severe to discontinue the infusion, subsequent infusions may be administered with premedication at the discretion of the investigator, following agreement with the Lilly CRP or clinical pharmacologist
- If a participant's infusion rate is reduced due to an infusion reaction, subsequent infusions may be administered at the discretion of the investigator, following agreement with the Lilly CRP or clinical pharmacologist. If further infusions are administered, the infusion rate must not exceed the slowest rate used to complete the infusion on the occasion when the infusion reaction occurred. Premedication may be administered at the discretion of the investigator.
- If it is determined that the participant should not receive further doses of the investigational product, the participant should complete AE and other follow-up procedures per the SoA (Section 1.3) of this protocol.

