7.3. Lost to Follow-up

A participant will be considered lost to follow-up if he or she repeatedly fails to return for scheduled visits and is unable to be contacted by the study site. Site personnel or designee are expected to make diligent attempts to contact participants who fail to return for a scheduled visit or were otherwise unable to be followed up by the site.

Site personnel, or an independent third party, will attempt to collect the vital status of the participant within legal and ethical boundaries for all participants randomized, including those who did not get the investigational product. Public sources may be searched for vital status information. If vital status is determined to be deceased, this will be documented, and the participant will not be considered lost to follow-up. Sponsor personnel will not be involved in any attempts to collect vital status information.

8. Study Assessments and Procedures

Study procedures and their timing are summarized in the SoA (Section 1.3).

- Immediate safety concerns should be discussed with the sponsor immediately upon occurrence or awareness to determine if the participant should continue or discontinue study intervention.
- Adherence to the study design requirements, including those specified in the SoA, is essential and required for study conduct.
- All screening evaluations must be completed and reviewed to confirm that potential participants meet all eligibility criteria. The investigator will maintain a screening log to record details of all participants screened and to confirm eligibility or record reasons for screening failure, as applicable.
- Section 1.3 lists the SoA, detailing the study procedures and their timing (including tolerance limits for timing). The specifications in this protocol for the timings of safety and sample collection are given as targets to be achieved within reasonable limits. Modifications may be made to the time points based on emerging clinical information. The scheduled time points may be subject to minor alterations. However, the actual time must be correctly recorded in the CRF.
- Appendix 2 (Section 10.2) lists the laboratory tests that will be performed for this study.
- Appendix 2 (Section 10.2.1) provides a summary of the maximum number and volume of invasive samples, for all sampling, during the study.

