8.2.8.1.3. Study Drug Interruption or Discontinuation

If a participant develops any one of the following laboratory or clinical changes, interrupt the study-drug and continue close monitoring and comprehensive hepatic evaluation as described in Section 8.2.8.1.1. and 8.2.8.1.2.

ALT or AST ≥3x ULN with hepatic signs/ symptoms ^a or	
ALT or AST ≥5x ULN for more than 2 weeks or	
ALT or AST ≥8x ULN or	
ALT or AST $\geq 3x$ ULN and TBL $\geq 2x$ ULN ^b or INR ≥ 1.5 or	
ALP ≥3x ULN or	
$ALP \ge 2.5x \text{ ULN and TBL} \ge 2x \text{ ULN}^b \text{ or}$	
ALP ≥2.5x ULN with hepatic signs or symptoms ^a	

Examples of hepatic signs or symptoms: severe fatigue, nausea, vomiting, right upper quadrant abdominal pain, fever, rash, and/or eosinophilia >5%.

Interruption or discontinuation of study drug should include the following actions:

- While the participant is not receiving the study drug, clinical and laboratory monitoring should continue at a frequency of 1 to 2 times weekly until liver tests normalize or return to approximate baseline values.
- If the hepatic event continues past the anticipated end of the study (that is, data lock), the investigator should consult with the Lilly-designated medical monitor to determine the need for further data collection beyond the end date of the study (that is, data lock date).
- All the medical information and test results related to close hepatic monitoring and comprehensive hepatic evaluation should be collected and recorded in a hepatic safety CRF.
- Resumption of the study drug after interruption for a hepatic reason can be considered only in consultation with the Lilly designated medical monitor, only if the liver test results returned to near baseline, and if a self-limited non-study-drug etiology is identified. Otherwise, the study drug should be permanently discontinued.

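### The ocular restart sentence in Section 7.1.4 is ambiguous: read literally, its and/or lets Part B dosing resume while an interruption criterion is still met

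*Protocol*

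**What the plan says.** Protocol Section 7.1.4 opens with "The following criteria will lead to study intervention interruption" and lists three criteria joined by *or*: a rise of more than 10 points over baseline, a pressure above 25 mmHg, or signs of glaucoma. The two pressure criteria must be confirmed by a further consecutive assessment before treatment is given. The signs criterion carries no pressure threshold. The section closes with "Therapy may resume when ocular pressure is within normal limits and/or sign of glaucoma resolve". It does not define normal limits and does not tie either restart condition to the criterion that caused the interruption.

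Two general provisions also bear on the decision. Section 7.1 allows permanent discontinuation "for safety reasons, in the opinion of the investigator, or", and the opening of Section 8 states "Immediate safety concerns should be discussed with the sponsor immediately upon occurrence or awareness to determine if the participant should continue or discontinue study intervention".

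**The concern.** The stop rule is mandatory on any one finding, but the restart rule, as worded, can be met by clearing only one of two. A patient interrupted solely for glaucoma signs, with normal pressure, would meet the restart condition at once. A patient whose signs have resolved would meet it with pressure still past a limit.

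The study drug carries a glucocorticoid payload, and Section 2.3 names systemic glucocorticoid exposure among the key safety concerns. The ocular criteria were added to answer regulatory comments. In a multicenter first-in-human study, what is at stake is that sites apply one restart rule and that it does not contradict the stop rule.

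**Working it through.** No published figure needs reproducing; this is a check of wording.

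**Inputs.** The three criteria and the restart sentence come from Section 7.1.4. Assumptions: *points* means mmHg, and a pressure above 25 mmHg is outside normal limits.

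**Step 1: a participant who has or had signs.** Compare what still stands with what each reading allows.

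| Signs now | Pressure now | Criterion still met | Restart under *or* | Restart under *and* | Restart under the proposed sentence |
|---|---|---|---|---|---|
| Persist | Normal | Signs | Yes | No | No |
| Persist | Above normal | Signs, perhaps pressure | No | No | No |
| Resolved | Normal, not >10 over baseline | None | Yes | Yes | Yes |
| Resolved | Normal, >10 over baseline | Rise | Yes | Yes | No |
| Resolved | Above normal, neither limit passed | None | Yes | No | No |
| Resolved | Above normal, >25 mmHg or >10 over baseline | Pressure | Yes | No | No |

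The first row is case (1). The fourth and last rows are case (2). The fourth row also defeats plain *and*.

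**Step 2: can a pressure be normal and still more than 10 over baseline?** Let U be the upper limit of normal. The two overlap when baseline + 10 < U, that is, baseline < U − 10. The documents do not give U. If U = 21 mmHg (an assumption), a baseline of 10 and a current value of 21 give a rise of 11, which is normal yet past the relative limit. If U were 25, any baseline below 15 would leave room for overlap. If every baseline is at least U − 10, there is none. The same overlap can arise in a participant who never had signs: with nothing to resolve, restart needs only normal pressure, and the rise criterion may still be met.

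**Step 3: counts, which depend on Step 2.** Splitting pressure by normal or not, >25 mmHg or not, and >10 over baseline or not, the table rows hold 2 + 4 + 1 + 1 + 1 + 3 = 12 logical states.

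- Overlap possible: a criterion stands in 2 + 4 + 1 + 3 = 10 states. *Or* allows restart in 2 + 1 + 3 = 6 of them, *and* in 1, the proposed sentence in 0.
- Overlap impossible: one state leaves the first row and the fourth row disappears. A criterion stands in 8. *Or* allows restart in 4, *and* in 0, the proposed sentence in 0.

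These count combinations. They say nothing about how often each occurs.

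**Step 4: other restart rules in the protocol.**

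- Serious or opportunistic infection (7.1.5.2): withhold until "resolution of all acute clinical signs and symptoms, and completion of all appropriate anti-infective treatment (exception for LTBI, noted below". Latent tuberculosis has its own route.
- Hepatic (8.2.8.1.3): "only if the liver test results returned to near baseline, and if a self-limited non-study-drug etiology is identified", with medical monitor consultation.
- Infusion reaction severe enough to discontinue the infusion (6.1.3): "subsequent infusions may be administered with premedication at the discretion of the investigator, following agreement with the Lilly CRP or clinical pharmacologist".
- Cohort stopping (7.1.1): "may resume only following written approval from the sponsor medical monitor".

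Each has joint conditions, a named sponsor step, or both. The ocular sentence has neither.

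**Step 5: reach.** Part A is a single dose, so restart does not arise. The readable Part C schedules show no ocular line. In both Part B schedules, ocular checks during dosing fall at Visits 4 and 6; the next is follow-up Visit 801, after the last dose at Visit 8. After a Visit 6 finding, doses remain at Visits 7 and 8 in one schedule and at Visit 8 in the other. The Amendment b summary says that only the pressure measurement is required at Visits 4 and 6, so case (1) may surface less often there.

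**The case against.** The strongest reply is that *and/or* simply mirrors the list of triggers: pressure must normalize if pressure caused the interruption, signs must resolve if signs did, and both if both did. That is plausible and removes cases (1) and (2) when only one criterion was met. It is not written, however, and it does not cover a second criterion met after the first. Nor does it close the overlap in Step 2, because the stated condition is normal pressure and not clearance of the rise criterion.

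Second, the criteria stay in force. Interruption is mandatory and resumption only permitted, so a confirmed raised pressure would stop dosing again. This has force for case (2), provided someone measures; no ocular check is scheduled between Visit 6 and the end of dosing, though unscheduled checks remain possible. It helps less in case (1), because a criterion worded as developing signs does not clearly trigger again for signs that never went away.

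Third, there are safeguards. Investigator judgment (7.1) and sponsor discussion (Section 8) apply. If pressure-lowering medication were needed, Section 6.9 leaves continuation to the investigator after sponsor consultation. Section 8.3 requires medically important or related events to be followed. Exclusion criterion 37 keeps out pre-existing glaucoma, though only at entry. These reduce the consequence, but none sets a minimum condition for restart.

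Fourth, Section 8.2.4 and the schedule comments are redacted. The amendment summary describes only examination windows for 8.2.4, so a restart rule there can be neither confirmed nor excluded. That limitation stands.

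**Conclusion.** The concern holds as an ambiguity. Read literally, Section 7.1.4 permits restart in Part B while glaucoma signs persist with normal pressure, or after signs resolve with pressure still past a limit, and no readable text sets a floor. Changing *and/or* to *and* would remove most of the conflict, but not the normal-yet-more-than-10-over-baseline state if the normal range allows it.

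A reader might infer that the protocol knowingly licenses dosing in patients with active glaucoma, or might take 6 of 10 as a risk. The documents support neither: a benign reading is available, resumption is discretionary, and the counts carry no probabilities and shift with an undefined normal range.

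The conclusion rests on the literal reading, on >25 mmHg lying outside normal limits, and on the readable text alone. The reach is essentially Part B repeat dosing, and no endpoint, estimate or other statistical result is affected. It is worth correcting because it is a safety rule and the correction is cheap.

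**What to change.** Replace the last sentence of Section 7.1.4 with: *Therapy may resume only when ocular pressure is within normal limits, any signs of glaucoma have resolved, and no interruption criterion above is still met.* The final clause closes the overlap that plain *and* leaves open, whatever the normal range.

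The drafting cost is one sentence. The clinical cost is possibly a few more withheld doses, notably when signs have resolved and pressure is above normal but past neither limit. No criterion stands in that state, yet dosing would wait, and a patient whose pressure habitually sits there might not restart. The sponsor should accept that consequence knowingly.
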